**Study visits and procedures are detailed in the study table in the Appendix.**

### **3.2 Selection of Patients**

The total number of patients to be treated in this study is up to 64 patients (48 total patients dosed at 3 mg).

#### **3.2.1 Inclusion Criteria**

Each patient must meet all of the following inclusion criteria to be enrolled in the study:

1. Patient must have undergone autologous stem cell transplantation, with melphalan as a preparative regimen, within 12 months of initiation of induction therapy for newly diagnosed myeloma.
2. Time to initiation of maintenance therapy.

Patients may start maintenance therapy as early as 60 days post transplant and up to - 180 post transplant; as long as they meet the following criteria:

- Platelet count  $\geq$  100,000/mm^3
- Neutrophil count  $\geq$  1000/mm^3. (No growth factors within 5 days)
- Total bilirubin  $\leq$  1.5  $\times$  ULN
- Alanine aminotransferase (ALT) and aspartate aminotransferase (AST)  $\leq$  3  $\times$  ULN
- Creatinine  $<$  2.5 mg/dL
- Recovered (ie,  $\leq$  Grade 1 toxicity) from the reversible effects of autologous

3. Patients whose primary therapy was changed due to suboptimal response or toxicity will be eligible, however no more than 2 regimens will be allowed prior to ASCT.

4. Male or female patients 18 years or older.

5. Patients must have an Eastern Cooperative Oncology Group (ECOG) status of 0 to 2.

6. Voluntary written informed consent before performance of any study-related procedure not part of normal medical care, with the understanding that consent may be withdrawn by the subject at any time without prejudice to future medical care.

7. Female patients who:

- Are postmenopausal for at least 1 year before the Screening visit, OR
- Are surgically sterile, OR
- If they are of childbearing potential, agree to practice 2 effective methods of contraception, at the same time, from the time of signing the informed consent, during study treatment and for 28 days after the last dose of study treatment, OR agree to completely abstain from heterosexual intercourse

Male patients, even if surgically sterilized (ie, status postvasectomy), who:

- Agree to practice effective barrier contraception during the entire study treatment period and through 28 days after the last dose of study treatment, OR
- Agree to completely abstain from heterosexual intercourse

## 3.2.2 Exclusion Criteria

Patients meeting any of the following exclusion criteria are not to be enrolled in the study:

1. Patient has  $\geq$  Grade 2 peripheral neuropathy.
2. Major surgery within 14 days before the first dose of study drug.

3. Radiotherapy within 14 days before enrollment
4. Known active central nervous system involvement
5. Systemic treatment, within 14 days before study enrollment, with strong inhibitors of CYP1A2 (fluvoxamine, enoxacin, ciprofloxacin), strong inhibitors of CYP3A (clarithromycin, telithromycin, itraconazole, voriconazole, ketoconazole, nefazodone, posaconazole) or strong CYP3A inducers (rifampin, rifapentine, rifabutin, carbamazepine, phenytoin, phenobarbital), or use of Ginkgo biloba or St. John's wort
6. Inability to swallow oral medication, inability or unwillingness to comply with the drug administration requirements, or GI procedure that could interfere with the oral absorption or tolerance of treatment.
7. Evidence of current uncontrolled cardiovascular conditions, including uncontrolled hypertension, uncontrolled cardiac arrhythmias, symptomatic congestive heart failure, unstable angina, or myocardial infarction within the past 6 months.
8. Female subject is pregnant or lactating.
9. Serious medical or psychiatric illness that could, in the investigator's opinion, potentially interfere with participation or completion of treatment according to this protocol.
10. QTc B > 470 milliseconds (msec) on a 12-lead ECG obtained during the Screening period. If a machine reading is above this value, the ECG should be reviewed by a qualified reader and confirmed on a subsequent ECG.
11. Ongoing or active systemic infection, known human immunodeficiency virus (HIV) positive, known active hepatitis B virus hepatitis, or known active hepatitis C virus hepatitis.
12. Infection requiring systemic antibiotic therapy or other serious infection within 14 days before study enrollment.
13. Known allergy to any of the study medications, their analogues, or excipients in the various formulations.

14. Participation in clinical trials with other investigational agents not included in this trial, within 21 days of the start of this trial and throughout the duration of this trial.
15. Failure to have fully recovered (ie,  $\leq$  Grade 1 toxicity) from the effects of prior chemotherapy regardless of the interval since last treatment.
16. Co-morbid systemic illnesses or other severe concurrent disease that, in the judgment of the investigator, would make the patient inappropriate for entry into this study or interfere significantly with the proper assessment of safety and toxicity of the prescribed regimens.

### **3.3 Study Treatments**

#### **3.3.1 Clinical Trial Materials**

##### **MLN9708**

MLN9708 will be provided by Millenium at no cost.

##### **Lenalidomide (REVLIMID®)**

Lenalidomide (REVLIMID®) is commercially available oral drug supplied in 25mg, 10mg and 5mg capsules.

#### **3.3.2 Preparation, Handling, Storage, and Destruction of Drugs**

##### **Drug Administration**

###### **Lenalidomide (Revlimid®) Administration:**

For study participants, commercial supply of lenalidomide will be utilized and administered through the RevAssist® program.

Women of childbearing potential should not handle or administer the clinical dosage forms unless they are wearing gloves.

**Only enough lenalidomide for 1 cycle may be provided to the patient each cycle.**

If a dose of lenalidomide is missed, it should be taken as soon as possible on the same day. If it is missed for the entire day, it should not be made up.

Patients who take more than the prescribed dose of lenalidomide should be instructed to seek emergency medical care if needed and contact study staff immediately.

Accurate records will be kept in the source documents of all drug administration (including prescribing and dosing).

Research center personnel will review the dosing instructions with subjects. Subjects will be asked to maintain a diary to record the drug administration. Subjects will be asked to bring any unused drug and empty drug containers to the research center at their next visit. Research personnel will count and record the number of used and unused drug at each visit and reconcile with the patient diary.

MLN9708

All protocol-specific criteria for administration of study drug must be met and documented before drug administration. Patients should be monitored for toxicity, as necessary, and doses of MLN9708 should be modified as needed to accommodate patient tolerance to treatment; this may include symptomatic treatment, dose interruptions, and adjustments of MLN9708 dose (see Section 3.3.3) and per PI discretion.

### **MLN9708 Administration**

Capsules of MLN9708 will also be referred to as study drug. Study drug will be supplied by Millennium as capsules of 0.2, 0.5, and 2.0 mg MLN9708.

The prescribed administration of MLN9708 doses in this study is 3 mg MLN9708 on days 1, 8, 15 on a 28 day cycle.

Patients should be instructed to swallow MLN9708 capsules whole, with water, and not to break, chew, or open the capsules. Study drug should be taken on an empty stomach (no food or drink) at least 1 hour before or 2 hours after a meal. Each capsule should be swallowed separately with a sip of water. A total of approximately 8 ounces (240 mL) of water should be taken with the capsules.

Missed doses can be taken as soon as the patient remembers if the next scheduled dose is 72 hours or more away. A double dose should not be taken to make up for a missed dose. If the patient vomits after taking a dose, the patient should not repeat the dose but should resume dosing at the time of the next scheduled dose.

**MLN9708 Destruction**

Investigational MLN9708 (expired or end of study) should be destroyed on site according to the institution's standard operating procedure. Be sure to document removal and destruction on drug accountability logs.

**3.3.3 Dose Modification and Delay**

**Before each cycle the patient will be evaluated for possible toxicities that may have occurred after the previous dose(s). Toxicities are to be assessed according to the NCI Common Toxicity Criteria for Adverse Events (CTCAE), Version 4.0 (<http://ctep.cancer.gov/reporting/ctc.html>).** Each AE should be attributed to a specific drug, if possible, so that the dose modifications can be made accordingly. If multiple toxicities are noted, the dose adjustments and/or delays for lenalidomide and MLN9708 are per PI discretion and suggest refer to guidelines that address the most severe toxicity.

**3.3.3.1 Criteria for Beginning or Delaying a Subsequent Treatment Cycle**

Treatment with Lenalidomide and MLN9708 will use a cycle length of 28 days. For a new cycle of treatment to begin, the patient must meet the following criteria:

- ANC must be  $\geq$  1,000/mm^3.
- Platelet count must be  $\geq$  75,000/mm^3.

In addition, all other toxicity considered to be related to treatment with MLN9708 must have resolved to  $\leq$  Grade 1, to the patient's baseline values, or to a level considered acceptable by the physician (eg, hypokalemia that can be managed by replacements) before a new cycle of MLN 9708 treatment may begin.

If greater than  $> 4$  week delay in starting subusequent cycle due to recovery from toxicity, consider dose reduction in attributable drug.

If the patient fails to meet the above-cited criteria for initiation of the next cycle of treatment, dosing should be delayed until recovery. The maximum delay before treatment should be discontinued will be 6 weeks or at the discretion of the Principal Investigator.

Intracycle dosing :

Lenalidomide should be held if plt < **If platelet count  $\leq 30 \times 10^9/\text{L}$  or ANC  $\leq 0.75 \times 10^9/\text{L}$**   
**If platelet count  $\leq 30 \times 10^9/\text{L}$  or ANC  $\leq 0.75 \times 10^9/\text{L}$  until recovered to platelet > 75,000 and ANC > 1.0**

**Suggested Dose Modification patients if on Lenalidomide 10 mg**

	Lenalidomide	MLN 9708
Dose -1	unchanged	2.4 mg
Dose -2	10 mg q 21	2.4 mg
Dose -3	10 mg q 21	1.5 mg
Dose -4	5 mg q 21	1.5 mg

**Suggested Dose Modification If on lenalidomide 15 mg**

After 3 cycle is if the Lenalidomide has been increased to 15 mg daily use the following dose modification:

	Lenalidomide	MLN 9708
Dose -1	10 mg q 28	3mg
Dose -2	10 mg q 28	2.4mg
Dose -3	10 mg q 21	2.4mg
Dose -4	10 mg po q 21	1.5mg
Dose -5	5 mg q 21	1.5mg

For dosing recommendations upon recovery, refer to Table 3-2 and Table 3-3.

**Table 3-1 Dose Reduction Steps for MLN9708**

Starting Dose	First Dose Reduction	Second Dose Reduction	Third Dose Reduction
3.0 mg	2.4mg	1.5mg	Discontinue MLN9708

### 3.3.4 Dose Adjustments for Hematologic Toxicity

#### MLN9708 Dose Adjustments for Hematologic Toxicity

Dosage adjustments for hematologic toxicity are outlined in Table 3-2.

**Table 3-2 MLN9708 Dose Adjustments for Hematologic Toxicities**

Criteria	Action
Within-Cycle Dose Modifications	

 
If platelet count <math>\leq 30 \times 10^9/L</math> or ANC <math>\leq 0.75 \times 10^9/L</math> on a MLN9708 dosing day (other than Day 1)
 
	
 
MLN9708 dose should be withheld.
 
Complete blood count (CBC) with differential should be repeated as clinically indicated
 
Upon recovery, MLN9708 may be reinitiated with 1 dose level reduction.
 

•	•
Dose Modifications for Subsequent Treatment Cycles	

 
All hematologic toxicities
 
	
 
For hematologic toxicity that occurs during a cycle but recover in time for the start of the next cycle,: 
 
If dose was reduced within the cycle, start the next cycle at that same dose.
 
If due to toxicity timing, ie, after Day 15 dosing thus a dose reduction was not required at that point in the cycle, reduce MLN9708 by 1 dose level at the start of that cycle.
 
Do not reduce the dose both within a cycle and at the start of the cycle for the same most severe toxicity.
 
 
 

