### **3. INVESTIGATIONAL PLAN**

#### **3.1 Overall Design and Plan of the Study**

Eligible patients will be enrolled and maintenance therapy on protocol no less than 60 days and must be initiated no more than 180 days post ASCT.

Patients will have standard restaging studies prior to initiation of therapy.

Standard post transplant therapy per institutional guidelines will be unaltered including prophylaxis therapy, vaccinations and restaging.

Patients who have completed ASCT and meet eligibility criteria will initiate maintenance therapy based on time on enrollment either in the phase dose escalation or expansion portion of trial.

Patients' clinical laboratory values and toxicity must be as specified below within 5 days before the first dose of study drug:

- Platelet count  $\geq 100,000/\text{mm}^3$
- Neutrophil count  $\geq 1000/\text{mm}^3$  (No growth factors within 5 days)
- Total bilirubin  $\leq 1.5 \times \text{ULN}$
- Alanine aminotransferase (ALT) and aspartate aminotransferase (AST)  $\leq 3 \times \text{ULN}$
- Creatinine  $< 2.5 \text{ mg/dL}$

Recovered (ie,  $\leq$  Grade 1 toxicity) from the reversible effects of autologous stem cell transplant.

Each cycle will be defined as a 28 day cycle. Drug holidays and break in therapy including those due to holidays, physician discretion and drug delivery are allowed as needed. Study drug will begin at Lenalidomide (10 mg/day); after three cycles , provided the ANC is  $\geq$  1000/ $\mu$ L, platelet count  $\geq$  100,000/ $\mu$ L, and all nonhematologic toxicity is  $\leq$  grade 1, then the dose may be increased to 15 mg/day at discretion of physician.

MLN 9708 will be dosed at 3 mg flat dose on days 1, 8, 15 administered orally.

Patients will be allowed to receive radiotherapy for palliation of symptoms during the course of maintenance therapy

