## 8. APPENDICES

### 8.1 Study Flow Chart

Procedure	Screening ≤ 28 days from Initiation of therapy (may include Day 1)	Baseline	Cycle 1: (except cycle 1 day 1  ) 			all cycles beyond cycle 1		End of study	Follow up
			Cycle 1 Day 1 +/- 7 days	Day 8 +/-3 days (only dose escalation phase)	Day 15 +/-3 days ( only dose escalation phase)	Day 1 +/-7 days			
Informed consent	X								
Inclusion/Exclusion criteria	X								
Complete Medical Hx	X								
Confirmation Dx and status of disease and prior Rx	X								
MDASSI Questionnaire and Correlative Samples 		X					X 		
Record concurrent therapies/procedures	X								
Record adverse events	X	X					X	X	
Physical examination, vital signs Score 	X	X	X	X			X	X	
Skeletal survey( as clinically indicated)	X							X	
Bone Marrow aspiration and biopsy	X						X 	X	
12 Lead ECG	X								
Hematology 	X 	X	X	X			X	X	
Serum chemistry 	X 	X	X	X			X	X 	
TSH	x								
Ht, Wt, BSA	X	X					X	X	
Pregnancy test for females of child bearing potential	X	X 					X 	X	
Register Patient into Rev Assist® Program	X								
Serum and urine M component quantification	X						X (every 1-3 cycles)	X	
24hour urine for protein measurement	X						X (every 1-3 cycles)	X	
Prescribe lenalidomide via RevAssist®		X					X		
Serum for FreeLite Testing	x						X (every 1-3 cycles)	X	
Dispense study drug for next cycle		X					X		
Perform drug accountability			X				X	X	
Survival status									X 

1. A repeat bone marrow biopsy will only be done at time of suspected complete remission to document complete remission per standard clinical practice and at physician discretion.
2. To include Na, K, Cl, Co2, Ca, Mg, Phosphorous, BUN, Cr., glucose, albumin, alk phos, total Bili, ast/alt.
3. WBC, differential, Hgb, Hct and platelet count
4. Screening CBC and Chemistry parameters need to meet criteria to initiate dosing in section 3.1 within 5 days of starting protocol directed therapy.
5. Pregnancy testing will be done 10-14 days prior to starting therapy and within 24 hours prior of starting lenalidomide on day 1
6. These will be done every 1-3 cycles.

**7. DAY 8 AND DAY 15 (+/- 3 DAYS ASSESSMENTS ARE TO BE DONE DURING CYCLE 1 AND DURING THE CYCLE THE PHYSICIAN DOSE ESCALATES**

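### In routine later cycles the within-cycle blood-count holds have no scheduled count behind them, and the flow chart contradicts itself on who has mid-cycle counts in cycle 1

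*Combined protocol and SAP*

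**What the plan says.** MLN9708 is given as "3 mg MLN9708 on days 1, 8, 15 on a 28 day cycle" (MLN9708 Administration). The provisions that matter here are these.

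- **Table 3-2, within-cycle rule.** MLN9708 is withheld if platelets are at or below 30 x 10^9/L or ANC is at or below 0.75 x 10^9/L "on a MLN9708 dosing day (other than Day 1"). After a hold, "Complete blood count (CBC) with differential should be repeated as clinically indicated", and the drug may restart one dose level lower.
- **Table 3-2, next-cycle rule.** If toxicity arises after the Day 15 dose and has recovered by the next cycle, MLN9708 is reduced one level at the start of that cycle.
- **Section 3.3.3.1, lenalidomide.** Under intracycle dosing, "Lenalidomide should be held if plt <" introduces the same two limits. No day is named.
- **Section 3.3.2.** "All protocol-specific criteria for administration of study drug must be met and documented before drug administration".
- **Flow chart, section 8.1.** Cycles after the first have one visit column, Day 1 +/- 7 days, with hematology marked. The Day 8 and Day 15 columns under cycle 1 are headed "only dose escalation phase". Footnote 7 says that Day 8 and Day 15 "ASSESSMENTS ARE TO BE DONE DURING CYCLE 1 AND DURING THE CYCLE THE PHYSICIAN DOSE ESCALATES".
- **Section 3.4, Thrombocytopenia and Neutropenia.** Counts follow the protocol's schedule, and further tests may be ordered under usual clinical practice.
- **Section 5.** The toxicity stopping endpoint includes grade 4 hematologic effects that require delay or termination of treatment in cycle 1. Toxicity is otherwise summarized in frequency tables, with no stated split by period.

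**The concern.** A hold that depends on a count on a given day needs a count on that day. If the schedule does not supply one, the rule works only for patients whose clinician happened to order a test. Two patients with the same counts could then be handled differently. The difference can last, because a hold leads to a lower restart dose and the note after Table 3-3 bars re-escalation.

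The reporting follows the same path. Section 4.1 treats an abnormal laboratory value as an adverse event only if it leads to action or is judged clinically significant. A count that is not drawn can do neither. Frequency tables that pool cycle 1 with later cycles therefore mix two levels of ascertainment.

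Cytopenia is not a remote possibility. Section 1.4 cites 43% grade 3/4 neutropenia and 13% grade 3/4 thrombocytopenia in a randomized trial of lenalidomide maintenance. Tolerability and toxicity are stated objectives of this study.

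**Working it through.** The plan gives no figure to reproduce. The check sets each rule against the schedule and counts the scheduled tests. It relies on the flow chart's column headings and footnote text, not on the position of individual cell marks.

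**Step 1: days on which the MLN9708 rule can apply.** The dosing days are 1, 8 and 15. Removing Day 1 leaves 2 of the 3 doses in each cycle.

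**Step 2: scheduled counts on those two days.**

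| Cycle | Source | Scheduled counts |
|---|---|---|
| Cycle 1, footnote 7 governs | Footnote 7 | 2 of 2 |
| Cycle 1, column heading governs, patient outside the dose escalation phase | Day 8 and Day 15 headings | 0 of 2 |
| Cycle in which lenalidomide is escalated (possible only after three cycles, section 3.1) | Footnote 7 | 2 of 2 |
| Every other later cycle | Day 1 column only | 0 of 2 |

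Footnote 7 is marked on the physical-examination row. I read it as covering hematology too, which is the reading more favourable to the plan.

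**Step 3: gap after the Day 15 dose in a routine later cycle.** The next scheduled count is at Day 1 of the next cycle, which is Day 29. 29 - 15 = 14 days. With the +/- 7 day window, 14 - 7 = 7 to 14 + 7 = 21 days.

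**Step 4: the next-cycle reduction rule.** It concerns toxicity that appears after Day 15 dosing and has recovered by the next Day 1. No count is scheduled between those two points in any cycle, including cycle 1.

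**Step 5: lenalidomide.** The hold names no day and the drug starts as daily dosing ("Study drug will begin at Lenalidomide (10 mg/day" in section 3.1), so any count within the cycle can serve. In a routine later cycle none is scheduled after Day 1, and Day 1 has its own start criteria (ANC at least 1,000/mm3, platelets at least 75,000/mm3).

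**Step 6: scale over treatment.** Treatment length is not fixed, so the number of cycles n is an assumption. Non-Day-1 MLN9708 dosing days after cycle 1 = 2 x (n - 1), if no dose is missed.

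- n = 13: 2 x 12 = 24
- n = 26 (26 x 28 = 728 days, about two years): 2 x 25 = 50
- n = 39: 2 x 38 = 76

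In each case the number with a scheduled count is 0 without a lenalidomide escalation and 2 with one.

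**Step 7: the stopping rule.** It uses cycle 1 only, so sparse counts in later cycles leave its boundaries and Table 2 unchanged. The conflict between the column headings and footnote 7 does fall in cycle 1. If the headings govern, patients outside the dose escalation phase have no scheduled count between the Day 1 visits of cycles 1 and 2, and grade 4 hematologic events in that interval depend on unscheduled tests.

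**The case against.** The strongest reply is that Table 3-2 is conditional: it says what to do if a low count is seen and does not order a test. Its branch for toxicity after Day 15 has no scheduled count in any cycle, which suggests that it was written with unscheduled tests in mind. Section 3.3.2 follows its documentation sentence with monitoring as needed and leaves dose adjustment partly to the investigator. A full cycle of capsules is dispensed for home use, so a count before each dose may never have been intended. How often to draw blood in long maintenance is a clinical choice.

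Much of this stands, and it rules out several stronger readings that a reader might infer.

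- **That the holds cannot operate after cycle 1.** They can. Section 3.4 allows further tests, and footnote 7 adds Day 8 and Day 15 assessments in an escalation cycle.
- **That the lenalidomide hold needs Day 8 and Day 15 counts.** Section 3.3.3.1 names no day.
- **That Day 1 counts show toxicity only after an off-drug interval, near recovery.** The documents give no nadir or recovery times. Lenalidomide starts as daily dosing, and the stated terminal half-life of MLN9708 is about 5 to 7 days.
- **That later-cycle rates are known to be too low.** Adverse events are collected until 30 days after the last dose, not only at visits. Understatement is possible but not shown.

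The reply does not remove the mismatch. Permission to test is not a scheduled test, and section 3.3.2 asks for documentation before dosing. Nor does it answer the conflict between the column headings and footnote 7.

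**Conclusion.** The point holds as an inconsistency between the hold rules and the schedule. In routine later cycles, 0 of the 2 MLN9708 doses subject to the within-cycle rule has a scheduled count. The rule for toxicity after Day 15 has none between that dose and the next Day 1 in any cycle. The lenalidomide hold has none after Day 1 in routine later cycles. All three then rest on unscheduled tests. Separately, the flow chart gives two answers on who has Day 8 and Day 15 counts in cycle 1, which bears on finding grade 4 hematologic events for the stopping endpoint.

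Later-cycle hematologic rates may be understated; the documents do not allow the amount to be estimated. The printed stopping boundaries and their operating characteristics are not in question. The conclusion assumes that the column headings and footnote 7 mean what they say and that footnote 7 covers hematology. If it covers the physical examination only, the escalation cycle also lacks a scheduled mid-cycle count. The point is worth correcting because a stated safety rule is involved and the change is small.

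**What to change.** 1. Reconcile sections 3.3.2 and 3.3.3.1 and Table 3-2 with the flow chart's column headings and footnote 7, so that the hold rules and the scheduled counts refer to the same days, cycles and patients. Which rule or schedule should prevail is for the sponsor and investigators; this review takes no position.
2. In section 5, tabulate hematologic toxicity separately for cycle 1 and for later cycles. Beside each, state the scheduled counts and that unscheduled counts also contribute, and note that later-cycle rates may be understated. The later figures should not be described as Day 1 values, because unscheduled counts and clinically detected events also enter them.
3. State which patients had scheduled Day 8 and Day 15 counts in cycle 1 when the toxicity stopping endpoint is reported.

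The cost is protocol wording and one extra table split. The reporting change needs no added blood draws; those would arise only if the sponsor chose to extend the schedule.
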